9.1. Study design

This is a non-interventional, cross-sectional study to evaluate the effectiveness of RM tools for voriconazole. The study objectives will be accomplished by means of a cross-sectional, web-based survey of all HCPs who were targeted to receive the aRMMs and self-report as prescribers of voriconazole within 12 months preceding the survey in Saudi Arabia (Central, East and North regions). The study aims to obtain completed surveys from 10 HCPs. Data will be collected until 10 completed surveys are obtained or up to a data collection period of 60 to 90 days as a maximum. The data from the HCPs will be collected using a structured self-administered questionnaire to gather evaluation metrics related to the utilization and understanding of RM tool content and messages. In addition, the survey will assess behaviors, including a set of hypothetical scenarios for HCPs. The survey is not intended to be a mechanism for collecting adverse events (AEs), nor is it intended to result in minimizing the numbers of AEs reported. HCPs will be invited by e-mail to participate in the survey and asked to complete the online questionnaire.

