9.2.1. Inclusion criteria

Participants/ HCPs must meet all of the following criteria to be eligible for inclusion in the survey:

- 1. Willing/consent to participate in this self-administered survey.
- 2. Involved in the treatment of at least 1 patient with voriconazole within the last 12 months.

Evidence of an electronically signed and dated informed consent document indicating that the participant/ HCP has been informed of all pertinent aspects of the study.

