All questions must be answered in order to complete the survey. In each survey, response options presented in a list will be presented in random order (where appropriate) to minimise positional bias. Programming will be reviewed by quality control and simulated users (User Acceptance Testing) prior to implementing the survey.

2. Generalization of the survey results to the overall target population

In such surveys, the generalization and external validity of the results is restricted to HCPs who can be reached and are willing (and able) to answer a questionnaire online questionnaire. These HCPs may not be fully representative of the whole target population.

The study report will discuss the results in the light of the limitations described above including variability and uncertainty of the data and methods.

Redacted

Finally, the marketing authorization holder (MAH) acknowledges that an a priori threshold of 80% correct per risk questions will be used to define the success of the program. However as acknowledged by EMA, the selection of this threshold for success is subjective (7 May 2015 PRAC Rapporteur PASS Protocol Assessment Report; Procedure no.: EMEA/H/C/000387/MEA 087.2) and not based on a prior knowledge, experience, or established scientific criteria in the education or risk communication literature. The MAH expects that the knowledge may differ by key risk message, clinical practice, & HCP specialties. Moreover, sample size may not be sufficient to conduct subgroup or stratified analyses.

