21.		often do you perform a dermatologic evaluation when VFEND (voriconazole) ntinuously used despite the occurrence of phototoxicity-related lesions? Weekly Monthly Every two months
		On systemic and regular basis
		I do not know
22.		which of below condition(s) would you discontinue VFEND (voriconazole) in a nt? (Select the one best response).
		Phototoxicity
		Squamous Cell Carcinoma (SCC)
		Premalignant lesions
		All of the above

23. Did you or another staff member request additional copies of the VFEND (voriconazole) RM tools?

Redacted

Voriconazole A1501110 NON Version 1.0, 16	-INTERVENTIONAL STUDY PROTOCOL August 2024
	Yes
	No
[CLOSING	
	Thank you.

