Knowledge about the RM tools	Q7. According to the SPC/PI, the known risks for VFEND (voriconazole) are as follows: (Please select only one response for each of the risks listed in the table below.) Q8. Please select only one response for each statement about VFEND	Yes	Question completed correctly (6 points) Question completed correctly (5 points)	An HCP is considered successful for Knowledge when he/she provides at least 9 out of 11 (~80%) correct/desirable responses. Success for
Self-declared behavior/ Practice	(voriconazole) below: Q18. Which precautionary measures do you communicate to your patients for whom you	Yes	Question completed desirably (6 points)	Knowledge: if ≥80% of HCPs are successful An HCP is considered successful for awareness when he/she provides
	prescribe VFEND (voriconazole)? Please check all that apply. 18.a Do you, or another member of your healthcare team (e.g., nurse, pharmacist or other) perform each of these activities when initiating treatment with VFEND (voriconazole)? (Please check one response for each activity below).	Yes	Question completed desirably (6 points)	desirable responses to all sub-questions. Success for self-reported practices if ≥80% of HCPs are successful
	Q19. How frequently do you perform Liver Function Tests (specifically AST, ALT)?	Yes	Question completed desirably (Answer 1 is desirable)	

Q20. If there are no changes in Liver Function Tests (LFTs) after one month of initiation of VFEND (voriconazole), how often do you monitor liver function during VFEND treatment maintenance?	Yes	Question completed desirably (Answer 2 is desirable)	
Q21. How often do you perform a dermatologic evaluation when VFEND (voriconazole) is continuously used despite the occurrence of phototoxicity related lesions?	Yes	Question completed desirably (Answer 4 is desirable)	
Q22. For which of below condition(s) would you discontinue VFEND (voriconazole) in a patient? (Select the one best response).	Yes	Question completed desirably (Answer 4 is desirable)	

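### Q21 gives an HCP who has had no patient continuing voriconazole despite phototoxic lesions no fitting answer, and a don't-know reply there fails that HCP on the whole practice objective

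*Protocol*

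**What the plan says.** - **Eligibility.** Protocol section 9.2.1 asks only that the HCP was "Involved in the treatment of at least 1 patient with voriconazole within the last 12 months". The lowest patient-count band in Q13 (Annex 1.2) is 1–5. Nothing requires experience of phototoxicity.
- **The item.** Annex 1.5 lists "Q21. How often do you perform a dermatologic evaluation when VFEND (voriconazole) is continuously used despite the occurrence of phototoxicity related lesions". Annex 1.2 offers three fixed intervals, then "On systemic and regular basis", then a don't-know option. It has no free text, no not-applicable choice and no skip.
- **Mandatory reply.** Section 9.9.2 states "All questions must be answered in order to complete the survey". Section 10.3 treats an incomplete survey as a withdrawal.
- **Scoring.** For Q21, Annex 1.5 gives "Question completed desirably (Answer 4 is desirable"). The rule for the practice objective is "desirable responses to all sub-questions. Success for self-reported practices if ≥80% of HCPs are successful".
- **Scenarios.** Section 9.1 says that "the survey will assess behaviors, including a set of hypothetical scenarios for HCPs". Q22 is worded that way (what the HCP would do). Q21 asks what the HCP does.
- **Q22.** Its desirable answer is also the fourth, which covers all three listed conditions, phototoxicity among them.

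**The concern.** Q21 describes a doubly conditional situation: phototoxicity-related lesions have occurred, and voriconazole is still being given. An HCP who has treated one or a few patients may never have met it. Read literally, such an HCP has no accurate option. The nearest is the don't-know reply, which scores as undesirable, and under the all-items rule that alone makes the HCP unsuccessful on practice.

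An HCP with no occasion to act is then counted in the same way as an HCP whose practice departs from the SPC. An HCP who guesses, or who reports what they would do, supplies knowledge or intention where objective 4 (section 8) asks for self-reported practice. Either way, the practice proportion partly reflects who has met the situation and how they read the question.

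Q22 adds to the difficulty. An HCP who answers it as desired says that they would discontinue for phototoxicity, so they might be expected to have few or no patients in the situation that Q21 presupposes. The same HCP must nevertheless report practice in such patients in order to succeed.

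**Working it through.** **Inputs from the Protocol**
- Practice items (Annex 1.5): Q18 (6 points), Q18a (6 points), and Q19, Q20, Q21 and Q22, counted here as one each.
- HCP-level rule: all items desirable. Study-level rule: at least 80% of HCPs successful.
- Planned completed surveys: 10 (sections 9.1 and 9.5), described as an empirical size. There is no sample-size formula to reproduce.
- Knowledge rule, for comparison: at least 9 of 11.

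**The plan's own cut-offs**
- Knowledge: 0.8 × 11 = 8.8, rounded up to 9; 9/11 = 81.8%. This agrees with Annex 1.5 and tolerates two misses.
- Study level: 0.8 × 10 = 8 successful HCPs.

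**Effect on one HCP**
- Total points: 6 + 6 + 1 + 1 + 1 + 1 = 16.
- Q21 undesirable, all else desirable: 15/16 = 93.75%. The HCP is still unsuccessful, because the practice rule tolerates no miss.

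**Effect on the study-level criterion, n = 10**
- One such HCP: 9/10 = 90%, criterion met.
- Two: 8/10 = 80%, criterion met.
- Three: 7/10 = 70%, criterion missed whatever the other HCPs answer.

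**Illustration.** Let f be the share of HCPs who give a don't-know reply at Q21. The documents give no value for f, so the figures below are assumptions. HCPs are taken as independent, and X is the number among 10 who reply so:

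P(X ≥ 3) = 1 − [P(0) + P(1) + P(2)], with X binomial (10, f).

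| f (assumed) | P(X ≤ 2) | P(X ≥ 3) |
|---|---|---|
| 10% | 0.930 | 0.07 |
| 20% | 0.678 | 0.32 |
| 30% | 0.383 | 0.62 |
| 50% | 0.055 | 0.95 |

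If every other practice item is desirable, the middle column is also the probability that the objective is met. If HCPs who reply so for want of a patient were judged on the remaining 15 points, that probability would be 1 for any f, so the whole loss in this illustration comes from Q21.

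**Does the document handle applicability elsewhere?** Yes. In Annex 1.2, Q14 to Q17 and one line of Q18a appear only to HCPs who received or downloaded the tool concerned. Q21 has no such gate.

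**The case against.** The strongest reply is that Q21 can be answered by someone who has never had such a patient. Q14 to Q16 ask about the past 12 months, whereas Q21 uses the general present with no time window, so an HCP may truthfully report a standing practice. The questionnaire also shows something close to the desirable answer beforehand: the Checklist page displayed beside Q10 speaks of regular dermatologic evaluation when treatment continues, and an option in Q18 is worded much like the desired reply. This stands as far as it goes. The don't-know reply is one reasonable reading of the item, not the only truthful one, and prompting could push replies upward.

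Three stronger conclusions are therefore tempting but unsupported.
- *The practice proportion is biased downward.* Don't-know replies lower it, while prompted or intention-based replies raise it. The documents do not settle the net direction.
- *Most low-volume HCPs have no basis for an answer.* The Protocol gives no phototoxicity rate and no distribution of patient counts. Q21 is not limited to 12 months, so patient counts for that period understate experience.
- *Q20 has the same defect.* Q20 already opens with a condition and offers free text, so it needs no rewording on this ground.

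It is also true that section 9.7 reports each practice question separately and presents the response distributions, and that the 80% threshold is called subjective and is not formally tested. This makes the problem visible in the report but leaves the success rule unchanged. A don't-know reply can be seen there, but its reason cannot: nothing separates an HCP who has had no such patient from one who does not know.

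Finally, the all-items rule penalises any single miss, not only Q21. That is so, but Q21 differs in that the miss can arise from having had no occasion to act.

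**Conclusion.** The point holds for Q21. From the text alone, an HCP with no patient in the described situation who answers that they do not know is unsuccessful on the practice objective with 15 of 16 points desirable, and is indistinguishable in the success count from an HCP who departs from the SPC. Because others may guess or answer by intention, the item does not cleanly measure self-reported practice.

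A reader might infer that one such reply defeats objective 4 for the study. It does not: it fails one HCP, and three of 10 are needed to put the 80% criterion out of reach. The probabilities of 0.32 and 0.62 for that event rest on assumed reply rates of 20% and 30% and on independence between HCPs. They show sensitivity and are not a forecast.

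Q21's premise and Q22's desirable answer must be reconciled. No view is taken here on the clinical rule behind either. Question wording and scoring are fixed in Annexes 1.2 and 1.5, so this is not a matter left to the SAP. It is worth correcting before the survey is programmed.

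**What to change.** Change Q21 only, in one of two ways.

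1. Add an option such as 'I have had no such patient'. Add one line to Annex 1.5 saying that an HCP who chooses it is judged on the remaining practice items, and report the number not applicable. This keeps the item on actual practice. Its cost is a smaller denominator for Q21.
2. Word Q21 openly as a scenario ('If a patient ..., how often would you ...?'), in line with section 9.1 and with Q22. Every HCP can then answer. The small downside is that it measures intended rather than past practice, which the report should say.

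In either case, the sponsor should reconcile Q21's premise with Q22's desirable answer. The cost is one reworded question, or one added option with one scoring line.

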7. RATIONALE AND BACKGROUND

Voriconazole (Vfend®) is a broad spectrum triazole antifungal agent used in the treatment of a range of serious fungal infections in both inpatient and outpatient settings. The clinical benefit of voriconazole has been demonstrated for the treatment of invasive aspergillosis (IA), candidemia in non-neutropenic patients, fluconazole-resistant serious invasive Candida infections (including *Candida krusei*), and serious fungal infections caused by *Scedosporium* spp. and *Fusarium* spp. for which voriconazole is authorised for use in the Saudi Arabia. Voriconazole is also indicated in Saudi Arabia for the prophylaxis of invasive fungal infections in high risk allogeneic hematopoietic stem cell transplant (HSCT) recipients.

Phototoxicity, squamous cell carcinoma (SCC) of the skin, and hepatic toxicity have been designated as important 'identified' risks with administration of voriconazole in the Risk Management Plan (RMP) and are currently described in the Summary of Product Characteristics (SPC). To ensure that these risks are adequately managed, additional risk minimisation measures (aRMMs) across Saudi Arabia have been implemented in February 2023. These included updating the voriconazole SPC¹ with revisions to information on hepatotoxicity, phototoxicity, and SCC of the skin (routine risk minimisation activity), and developing a comprehensive educational programme at the point of patient care, intended to educate/remind healthcare professionals (HCPs) about the risks and how to manage them. These aRMMs target specialty care physicians who prescribe voriconazole (i.e., infectious disease physicians), and clinical pharmacists who manage the drug and its interactions (hereafter referred to as "HCPs"). The details of the Risk Minimisation (RM) tools for the education programme and how these tools are being implemented in Saudi Arabia are described in the RMP. The three components of the RM tools are the HCP Checklist, HCP Question & Answer (Q&A) Brochure, and Patient Alert Card. A brief description of each follows:

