Phototoxicity (eg, skin rash)			
Intestinal perforation			
Squamous cell carcinoma (SCC) of the skin			
Asthma			
Hepatic toxicity			
Cardiomyopathy			

8. Please select only one response for each statement about VFEND (voriconazole) below:

	True	False	I Don't Know
Long-term treatment (>6 months) with VFEND (voriconazole) should be considered only if the benefits outweigh the potential risks			
If phototoxic reactions occur, multidisciplinary advice should be sought and the patient should be referred to a dermatologist			
VFEND (voriconazole) should not be discontinued if premalignant skin lesions or skin Squamous Cell Carcinoma are identified			
Laboratory evaluation of hepatic function (specifically AST and ALT) at initiation and during the first month of treatment with VFEND (voriconazole) is not necessary			
If the Liver Function Tests become markedly elevated, VFEND (voriconazole) should be discontinued , unless the medical judgment of the risk-benefit balance of the treatment for the patient justifies continued use			

9.		you or your hospital receive the VFEND (voriconazole) Healthcare Professional P) Q&A Brochure?
		Yes
		No [GO TO Q10]
		I don't remember receiving it [GO TO Q10]
DISP	LAY '	THE FOLLOWING IMAGE ON THE SAME PAGE NEXT TO Q9]
		VFEND®(Voriconazole) Oral/Intravenous Healthcare Professional Question & Answer Brochure
		NFIDENTIAL Version 2, December 2022 SAU-0064 Page 2
9.1.	Did :	you read the VFEND (voriconazole) HCP Q&A Brochure ?
		Yes, all of it
		Yes, some of it
		No, I did not read it
		I don't remember reading it
		Redacted

Page 39 of 53

Voriconazole A1501110 NON-INTERVENTIONAL STUDY PROTOCOL Version 1.0, 16 August 2024

10.	Did you or your hospital receive copies of the VFEND (voriconazole) Healthcare
	Professional (HCP) Checklist?

Yes
No [GO TO Q11]
I don't remember receiving it [GO TO Q11]

|DISPLAY THE FOLLOWING IMAGE ON THE SAME PAGE NEXT TO Q10

VFEND® (Voriconazole) Healthcare Professional Checklist

Please complete this Checklist at each visit with your patient being treated with VFEND® (Voriconazole). Each of the three sections includes important risk information followed by a series of check boxes to help in the management of your patient for whom you prescribed VFEND.

A) Minimizing the Risk of Phototoxicity and Skin Squamous Cell Carcinoma

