- VFEND has been associated with phototoxicity and pseudoporphyria. It is recommended that all patients, including children, avoid exposure to direct sunlight during VFEND treatment and use measures such as protective clothing and sufficient sunscreen with high sun protection factor (SPF).
- The frequency of phototoxicity reactions is higher in the paediatric population. As an evolution towards SCC has been reported, stringent measures for the photoprotection are warranted in this population of patients. In children experiencing photoaging injuries such as lentigines or ephelides, sun avoidance and dermatologic follow-up are recommended even after treatment discontinuation.
- Squamous cell carcinoma (SCC) of the skin has been reported in patients taking VFEND, some of whom have reported prior phototoxic reactions.
- If phototoxic reactions occur, multidisciplinary advice (e.g. a consultation with a dermatologist) should be sought
 for the patient. VFEND discontinuation and use of alternative antifungal agents should be considered.
- Dermatologic evaluation should be performed on a regular basis whenever VFEND is continued, despite
 occurrence of phototoxicity-related lesions to allow early detection and management of premalignant lesions.
- VFEND should be discontinued if premalignant skin lesions or skin SCC are identified.
- SCC has been reported in relation with long-term VFEND treatment. Treatment duration should be as short as
 possible. Long- term exposure (treatment or prophylaxis) greater than 180 days (6 months) requires
 careful assessment of the benefit risk balance and physicians should therefore consider the need to limit
 the exposure to VFEND.
- For prophylaxis use, dose adjustments are not recommended in the case of lack of efficacy or treatment-related
 adverse events. In the case of treatment-related adverse events, discontinuation of VFEND and use of
 alternative antifungal agents must be considered.

Refer to the Summary of Product Characteristics for full prescribing and adverse event information.

Please review and answer the questions below for each patient receiving	og VEEND:
△ Has your patient developed phototoxicity? If YES, please refer to the Summary of Product Characteristics (SmP	YES NO
△ Have you arranged regular dermatologic evaluation for the patient presented with phototoxicity? If YES, please refer to the SmPC for further details. If NO, regular dermatologic evaluation should be arranged promptl details.	

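### Q21 asks how often the HCP performs a skin evaluation and offers no arrange, refer or team option, so an HCP who arranges it and reads the verb literally can be scored a practice failure

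*Protocol*

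**What the plan says.** - **The item.** Annex 1.5 lists Q21 among the scored practice questions: "How often do you perform a dermatologic evaluation when VFEND (voriconazole) is continuously used despite the occurrence of phototoxicity related lesions". Annex 1.2 gives five options: Weekly, Monthly, Every two months, "On systemic and regular basis" and I do not know. Annex 1.5 scores only the fourth as desirable.
- **The Checklist.** The page reproduced at Q10 in Annex 1.2 asks the HCP "Have you arranged regular dermatologic evaluation for the patient presented with phototoxicity". For phototoxic reactions it says that "multidisciplinary advice (e.g. a consultation with a dermatologist) should be sought". It also states, without naming who does it, "Dermatologic evaluation should be performed on a regular basis whenever VFEND is continued".
- **The knowledge item.** Row 2 of Q8 says that, after phototoxic reactions, "multidisciplinary advice should be sought and the patient should be referred to a dermatologist".
- **The respondents.** Section 7 describes the target group as "specialty care physicians who prescribe voriconazole (i.e., infectious disease physicians), and clinical pharmacists who manage the drug and its interactions". Q5 offers further specialties, two pharmacist categories and free-text entries.
- **Neighbouring items.** Q18a opens with "Do you, or another member of your healthcare team (e.g., nurse, pharmacist or other) perform each of these activities". Q19 and Q20 each offer an Other option with free text. Q21 has neither.
- **Scoring.** In the practice row of Annex 1.5 an HCP succeeds only if every sub-question is answered desirably, and the objective succeeds if at least 80% of HCPs do. Sections 9.1 and 9.5 aim for 10 completed surveys. Section 9.9.2 makes every question mandatory.

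**The concern.** Objective 4 is meant to estimate the proportion of HCPs whose practice agrees with the SPC. What matters for Q21 is whether regular skin evaluation takes place when treatment continues after phototoxicity. The stem instead asks about a personal act. It is a reasonable inference, though not a statement in the protocol, that some infectious disease physicians and clinical pharmacists arrange this evaluation and do not carry it out themselves.

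For such a respondent the answer depends on how the verb is read. Read loosely, the keyed option fits. Read literally, none of the three fixed intervals is true, the keyed option describes something the respondent does not personally do, and I do not know is the only way out of a mandatory question. That answer is scored as undesirable. The result is a misclassified HCP whose practice may be exactly what the Checklist asks for.

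Nothing later in the survey corrects this. Respondents cannot go back and edit (section 9.9.1), and no queries are sent to them (section 9.6).

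**Working it through.** **1. Wording, side by side**

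| Source | What the HCP is asked or told | Room for someone else to do it? |
|---|---|---|
| Q21 | how often the HCP performs the evaluation | none stated |
| Checklist question | whether the HCP has arranged it | yes |
| Checklist statement | it should be performed regularly (passive) | performer not named |
| Q18a | whether the HCP or a team colleague performs each activity | yes |
| Q19, Q20 | how often liver tests are done or monitored | Other, free text |

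The tools therefore use both verbs. Q21 takes up the passive sentence but turns it into a question about the respondent, and drops the safeguards used in Q18a, Q19 and Q20.

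**2. Effect on one HCP**

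The practice rule tolerates no miss. An HCP with every other practice item desirable and Q21 answered I do not know is a practice failure. By contrast, the knowledge rule in Annex 1.5 accepts 9 of 11, so it tolerates two misses.

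One reading is assumed here. The sentence in the practice row that sets the all-sub-questions rule says awareness. I read it as meaning practice, because it stands in that row and the next sentence sets the criterion for self-reported practices.

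**3. Effect on the study criterion**

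- Inputs from the protocol: n = 10 completed surveys; threshold 80%.
- Successes needed: 0.8 × 10 = 8. Failures tolerated: 10 − 8 = 2. A third practice failure, from whatever cause, misses the criterion.

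**4. Illustration under assumptions**

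The protocol states no probability for this criterion, so there is no figure of its own to reproduce. Two assumed quantities are needed: *s*, the share of HCPs who pass all other practice items, and *f*, the share who miss Q21 only because of the verb. Treating HCPs as independent, each succeeds with p = s(1 − f), and

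P(at least 8 of 10) = 45·p⁸(1 − p)² + 10·p⁹(1 − p) + p¹⁰.

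For s = 1:
- f = 10%, p = 0.9: 0.194 + 0.387 + 0.349 = 0.93
- f = 20%, p = 0.8: 0.302 + 0.268 + 0.107 = 0.68
- f = 30%, p = 0.7: 0.233 + 0.121 + 0.028 = 0.38

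| f | s = 1.00 | s = 0.90 |
|---|---|---|
| 0 | 1.00 | 0.93 |
| 10% | 0.93 | 0.71 |
| 20% | 0.68 | 0.44 |
| 30% | 0.38 | 0.22 |

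The row f = 0 is the position with the ambiguity removed. The table shows how sensitive the criterion is to a misread item. It does not predict how often the item will be misread.

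**The case against.** The case for leaving Q21 alone has real weight.

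- **The stem follows the Checklist.** Its verb, its condition and its keyed answer all track the sentence "Dermatologic evaluation should be performed on a regular basis whenever VFEND is continued". A reader might infer that Q21 contradicts the RM tools. It does not, because the tools speak of both performing and arranging. This stands.
- **The keyed option names no performer.** A reader might infer that a referring HCP has no true answer at all. That goes too far: an HCP who has arranged regular evaluation can naturally choose "On systemic and regular basis". Q19 uses the same verb for liver tests, where ordering the test is the ordinary meaning. This also stands, and only a literal reader is left without an accurate option.
- **Q8 concerns an earlier step.** Its referral advice applies when phototoxic reactions occur, whereas Q21 asks about evaluation when treatment continues afterwards. Q8 is therefore weak evidence of a mismatch.
- **Clarity testing is planned.** Section 9.9.1 says that the questionnaires will be tested for clarity. Testing might catch this, but a plan to test is no reason to leave a visible ambiguity in place.
- **The probabilities rest on an assumed share.** Correct. Moreover, what makes a single miss decisive is the all-sub-questions rule, which acts on every practice item and not on Q21 alone.

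The objection does not explain why Q21 alone lacks both the team wording and an open option, when the item must be answered and the respondents include clinical pharmacists.

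**Conclusion.** The point holds as an avoidable risk of misclassification in one scored item, and it is minor. One literal reading fails that HCP on practice. A reader might infer that it can also sink the objective for the study, but one such answer cannot do so when the other nine HCPs succeed; it takes three practice failures among ten.

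The size of the effect is unknown. The documents give neither the share of HCPs who arrange and do not perform the evaluation, nor the share of those who would read the verb literally. The figures of 0.93, 0.68 and 0.38 are conditional on assumed shares of 10%, 20% and 30%, on perfect answers elsewhere and on independence between HCPs.

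**What to change.** Reword the stem of Q21 in both Annex 1.2 and Annex 1.5, before programming, along these lines: *How often do you, or a colleague in your healthcare team, perform or arrange (for example by referral) a dermatologic evaluation when …*, with the rest of the stem as it is. Leave the response options and the scoring unchanged.

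The cost is one edited question stem, which can go through the clarity testing already planned. Sample size and analysis are unaffected, and no clinical rule is changed.
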